5. BACKGROUND AND RATIONALE

Psoriatic Arthritis (PsA) is an inflammatory arthritis estimated to occur in 15-30% of people with psoriasis[1] affecting around 150,000 people in the UK[2]. Audit data from Oxford in 2015 shows that 21.5% of patients in the early arthritis clinic have PsA. Two-thirds of people with PsA suffer progressive joint damage with associated disability[3, 4]. People with PsA have similar functional and quality of life impairment to rheumatoid arthritis[5]. PsA is associated with a reduced life expectancy[6] related to the risk of comorbidities, particularly the metabolic syndrome[7]. Direct costs to healthcare are estimated at £2,400 per patient annually in the UK with indirect costs (time lost from work and activities) per patient of over £8,000[8].

Treatment pathways in psoriatic arthritis are not well defined and have to be tailored to the individual given the heterogeneous nature of the condition. PsA can cause inflammation in joints, tendons, soft

tissues, skin, nails and spine in varying patterns. Different therapies are effective for different domains of disease so personalisation of therapy is paramount.

Very little is known about the decision to intensify treatment in PsA in routine practice. In recent years there has been an increasing focus on the idea of treating to target in PsA but this is not widely implemented. Research in Rheumatoid Arthritis (RA) has suggested that 60% of treatment change in RA is related to patient reported outcomes, compared to 40% related to doctor assessed clinical measures. [9]. We wish to study this influence in PsA.

The PsAID is a relatively new questionnaire developed by EULAR to measure patient impact in PsA. This disease-specific measure was developed with prominent patient involvement to ensure that all key physical, social and psychological domains are included. The PsAID-12 (with twelve questions) is designed for use in clinical practice and includes measures of pain, function, participation, sleep, depression, coping and anxiety. [10] It has provisional endorsement by the Outcome Measures in Rheumatology (OMERACT) group to measure health related quality of life and is now being used increasingly in observational and interventional studies. In observational studies of clinical practice, it has been shown to correlate with measures of disease activity and other measures of disease impact, however there has been much less research on the impact of its use in routine clinical practice.

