6. OBJECTIVES AND OUTCOME MEASURES

Objectives	Outcome Measures	Timepoint(s) of evaluation of this
------------	------------------	------------------------------------

		outcome measure (if applicable)
Primary objective		
Assess the influence of PsAID-12 score on likelihood of treatment escalation	PsAID-12 questionnaire Treatment escalation recorded in clinic, with reason for decision	Cross-sectional
Secondary objectives		
Evaluate the impact of reviewing the PsAID-12 questionnaire on the physician's decision to change treatment	Likert scale "Beyond your usual clinical assessment, how did your review of the patient's PsAID-12 questionnaire responses impact on your therapy decision for this patient"	Cross-sectional
Assess the effects of other factors that influence the likelihood of treatment escalation	Treatment escalation in clinic Factors include patient gender, disease duration, comorbidities, physician age, disease activity and PROs. Specifically addressing the impact of PsAID-12 individually and above other factors	Cross sectional
Determine which factors physicians feel influence treatment decisions in routine practice	NRS of the perceived importance of individual factors that may influence individual treatment decisions	Cross sectional
Evaluate patient satisfaction and perceived patient efficacy in the consultation and examine how this links to PsAID-12 score and change in treatment	CollaboRATE and PEPPi questionnaires and their relationship to PsAID-12 scores and treatment change	Cross sectional
Explore the physicians' views on the use and value of the PsAID-12 tool	Qualitative reports by physicians with themes identified retrospectively	

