11.3. Description of the Statistical Methods

A stratified estimate of the percentage of patients requiring an escalation in PsA treatment will be derived, with clinic as the stratum. For the primary outcome, logistic regression will be used to investigate the effect of the total PsAID-12 score on the probability of modifying treatment, after adjusting for clinic. This analysis will not take account of other possible predictive factors: see later paragraph in this section. The odds ratio will be estimated for unit increases in PsAID-12 score with associated 95% confidence interval.

Logistic regression will be used to investigate the relationship between various factors and the decision to change treatment. Potential factors to be investigated include:

- Patient characteristics (gender, disease duration, comorbidities, including presence of fibromyalgia)
- Physician characteristics (age)
- Disease activity characteristics (Patient global, physician global, joint counts, BSA, enthesitis, dactylitis)
- Disease impact characteristics (PsAID-12, Patient pain, HAQ, SF-36)

Various logistic regression models will be fitted to the data to identify the factors having most influence on the decision to escalate treatment. Once a suitable model has been identified, the term for PsAID-12 will be added to see its effect on that model. This will be done by assessing the goodness of fit of the models with and without PsAID-12, and also by estimating the odds ratio associated with a unit increase in PsAID-12 score, after fitting other predictive terms.

The collaboRATE scores will be used to assess the degree of patients' satisfaction with their consultation and the relationship between these scores and the decision to change treatment, and other key outcomes, will be investigated in summary tables and/or graphs.

The PEPPI scores will be used to assess the patients' own perceived level of confidence in interacting with the physician during the consultation. The relationship between these scores and the decision to change treatment, and other key outcomes, will be investigated in summary tables and/or graphs.

The characteristics of the patient population with regard to demographics, severity and duration of PsA and HRQoL, and characteristics of the participating centres (age/sex of physicians, country and type of centre), will be summarised in tables.

Other variables will be summarised in tables of descriptive statistics.

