11.4. Sample Size Determination

The initial sample size calculation was based on the need to estimate the percentage of patients for whom treatment is modified, with a stated degree of precision. This was defined as a 95% confidence interval for the percentage with width 10 percentage points (e.g. 25% to 35% for a percentage of 30%). This is based on data from the GRACE study which recruited 503 patients worldwide and found that 32%

underwent a treatment change, the majority escalation for active disease (Helliwell et al, ARD 2013; 72: 986). For a percentage of 30% (i.e. 30% of patients requiring treatment change), a study of 333 patients would have 80% power to estimate a percentage of 30% requiring change with a confidence interval of $\pm 5\%$ (Source: SAS® PROC POWER). A larger percentage of patients needing treatment change or a more precise estimate (narrower confidence interval) would require a larger sample size. For example, if the proportion requiring treatment escalation is 50%, then 390 patients would be required for the study to have at least an 80% chance of obtaining a 95% confidence interval of width 10 percentage points (i.e. 45% to 55%).

In order to investigate the effect of the total PsAID-12 score on the proportion, the sample size can be calculated using the method in Hsieh (1998). For example, if the effect of an increase in 1 s.d. of the PsAID-12 score is to increase the chance of intensifying the treatment from 30% to 40%, approximately 316 patients would be required for power of 95% and two-sided alpha of 5%

For the secondary outcome of assessing the importance of the various factors on an event (in this case the decision to intensify treatment), a rule of thumb is 10 patients experiencing the event per factor. If 15 factors affecting the decision to change treatment are to be investigated then this would require at least 150 patients requiring a treatment change, which for a percentage of 30% would need 500 patients in total. If the percentage requiring a treatment change is less than 30% then reliable estimates of the effect of fewer factors could be derived. Conversely, with a frequency of treatment change closer to 50% of patients, the effects of more factors could be estimated. It is likely that there could be some missing data but this will be checked carefully at source sites. There is no follow up required for this cross-sectional study so we have not accounted for loss to follow up.

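### PsAID-12 is tested last, on top of a data-chosen model that may already hold overlapping pain, function and global scores, so a null adjusted result could not be read as no influence

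*Combined protocol and SAP*

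**What the plan says.** Section 6 sets a secondary objective on the other factors that influence escalation, with the addition: "Specifically addressing the impact of PsAID-12 individually and above other factors". It counts disease activity and patient-reported outcomes (PROs) among those factors.

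Section 11.3 serves this objective by logistic regression. The candidate list includes "Disease impact characteristics (PsAID-12, Patient pain, HAQ, SF-36", and patient global stands under disease activity. Several models are then to be fitted to find the most influential factors, after which: "Once a suitable model has been identified, the term for PsAID-12 will be added to see its effect on that model". The effect is judged by comparing the goodness of fit of the models with and without PsAID-12, and by the adjusted PsAID-12 odds ratio. The section does not state whether PsAID-12 takes part in the selection step. It gives no selection rule and no handling of collinearity.

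Section 5 says that PsAID-12 "includes measures of pain, function, participation, sleep, depression, coping and anxiety", and that it correlates with measures of disease activity and impact. No coefficient is given.

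Section 11.4 sizes the PsAID-12 effect on its own. It sizes the multivariable analysis only by a rule of 10 events per factor.

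**The concern.** Two statisticians could follow Section 11.3 and run different analyses: one with PsAID-12 in the selection pool, one with it held back. If it is held back, selection can bring in pain, HAQ or patient global as stand-ins for PsAID-12, which is then adjusted for part of its own content.

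The objective also contains two questions: does PsAID-12 matter beyond what the physician assesses, and does it matter beyond the other PROs? A single odds ratio after data-driven selection answers a mixture that depends on which PROs happened to enter. If it came out null, the report might conclude that PsAID-12 does not influence escalation when the data show only that it shares content with pain and HAQ.

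**Working it through.** **Inputs from Section 11.4.** The assumed effect is that an "increase in 1 s.d. of the PsAID-12 score is to increase the chance of intensifying the treatment from 30% to 40" (percentages). The stated size is "approximately 316 patients would be required for power of 95% and two-sided alpha of 5" (per cent). The total of 500 comes from 15 factors × 10 events = 150 events, and 150/0.30 = 500.

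**Reproducing the plan's figure.** The odds ratio is (0.4/0.6)/(0.3/0.7) = 1.556, so the log odds ratio is 0.4418. Hsieh's formula for one continuous covariate gives

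n = (1.960 + 1.645)² / (0.30 × 0.70 × 0.4418²) = 317,

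which agrees with the stated 316. This calculation has no allowance for correlated covariates.

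**The added-last term.** Let R² be the share of the variance of PsAID-12 explained by the other terms. Then

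power = Φ(√[500 × (1 − R²) × 0.21] × 0.4418 − 1.96).

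At R² = 0.7 this is Φ(√31.5 × 0.4418 − 1.96) = Φ(0.52) = 70%. The factor by which the 95% limits lie above and below the odds ratio per SD is exp(1.96/√[500 × (1 − R²) × 0.21]).

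| Assumed R² | Power, full effect | Power, half the log odds ratio | 95% limit factor |
|---|---|---|---|
| 0 | 99.5% | 62% | 1.21 |
| 0.5 | 89% | 36% | 1.31 |
| 0.6 | 82% | 30% | 1.35 |
| 0.7 | 70% | 24% | 1.42 |
| 0.8 | 53% | 17% | 1.53 |
| 0.9 | 30% | 11% | 1.83 |

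With the full effect, 500 patients keep 80% power up to R² of about 0.62.

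**Simulation with a fixed set of three correlated covariates** (500 patients, 1,000 runs per setting, likelihood-ratio test). At R² of 0.54, 0.67, 0.77 and 0.80, power was 85%, 74%, 59% and 55% when the whole effect was direct, and 35%, 26%, 20% and 18% when half was. With no independent effect, the added-last test rejected in about 5% of runs, while PsAID-12 alone was significant in about 99%. So the added-last test is valid, and a significant result without the other PROs does not settle the incremental question.

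**Simulation with selection** (500 patients, 30% events, 1,000 runs per setting, forward selection at 0.05). PsAID-12 was the only true driver, and four correlated PROs had no effect of their own. The figures are the share of runs in which PsAID-12 was significant or selected.

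| Assumed R² | Held back, then added | Left in the pool | No PROs in the model |
|---|---|---|---|
| 0.51 | 90% | 94% | 99% |
| 0.70 | 68% | 85% | 99% |
| 0.91 | 28% | 69% | 99% |

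At R² 0.70, at least one PRO without effect was selected in 97% of the held-back runs. A second simulation of the same kind, with R² of 0.51, 0.63 and 0.75, selected such a PRO in 93% to 98% of runs and found PsAID-12 significant in 88%, 81% and 56% when held back. The two readings of Section 11.3 can therefore give different answers from the same data.

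**Limits.** R², the correlations and the independent share of the effect are all assumptions. The power formula and the first two simulations leave out adjustment for the 25 centres.

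**The case against.** The strongest reply is that adding PsAID-12 last is the standard test of incremental value and matches the stated objective. For a fixed covariate set, order of entry changes neither the likelihood-ratio test nor the adjusted odds ratio. This stands, and is why the fullest model stays in the fix. But Section 11.3 has no fixed set. What matters is that the other factors are chosen without PsAID-12.

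The natural reading is also that PsAID-12 is withheld from selection, since a term can be added only if it is not already in. That is fair: this is an ambiguity rather than a contradiction.

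The overlap is only partial. Section 5 also lists participation, sleep, depression, coping and anxiety, and names no global item. Pain, HAQ and patient global are only potential factors. Section 11.1 leaves detail to a separate SAP, which may settle some of this.

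Four stronger readings are tempting and not supported:

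- **That the test is null by construction.** It is not. That would need a very high R² or a small independent effect, and the documents show neither.
- **That goodness of fit means a lack-of-fit test such as Hosmer-Lemeshow.** No such test is named, and comparing models with and without a term ordinarily means deviance.
- **That a claim of 95% power fails.** Section 11.4 makes that claim for 316 patients and PsAID-12 alone, not for the adjusted term.
- **That a model without the other PROs should be the main answer.** Section 6 counts PROs among the other factors.

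**Conclusion.** The concern holds as a weakness in a secondary analysis. The stated procedure gives a clinic-adjusted odds ratio and one odds ratio after data-driven selection. Together they cannot tell an absent influence of PsAID-12 from one it shares with pain and HAQ.

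The size depends on an R² that the documents do not give. The loss of power is modest at an R² of 0.5 if the full planned effect survives adjustment, and substantial at 0.7 to 0.8. If only half the log odds ratio is independent of the other factors, power is 36% or less from R² 0.5 upwards. No power or precision is stated for the adjusted odds ratio, so the plan gives no basis for interpreting a null. The primary model, PsAID-12 with clinic, is not touched by this point.

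**What to change.** State in Section 11.3 and the SAP that PsAID-12 takes no part in choosing the base model, and replace the data-driven base model with three pre-specified ones. Clinic is handled in each as in the primary model.

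- **A:** patient, physician and physician-assessed disease activity factors, plus PsAID-12.
- **B:** the same factors without PsAID-12, plus pain, patient global, HAQ and the quality-of-life score actually collected (Section 9.7 lists EQ-5D-5L, whereas Section 11.3 names SF-36).
- **C:** B plus PsAID-12.

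Keep C as the answer to the stated objective. Report A beside it to show how much of the change in the PsAID-12 odds ratio comes with the overlapping PROs. Give 95% confidence intervals and the variance inflation factor. Compare B with C by a 1-df likelihood-ratio test on the same patients. State the precision expected at 500 patients over a range of R², and say that a null result in C alone will not be read as no influence.

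The cost is wording and a few extra fits on data already being collected. The downside is one more odds ratio to explain. Fixing the models also means counting their terms against the plan's own rule of 10 events per factor.

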3. SYNOPSIS

Study Title	How does PsAID implementation affect treatment intensification and patient satisfaction in PsA?		
Internal ref. no. / short title	AsseSSing Impact in pSoriatic Treatment (ASSIST) study		
Study registration			
Sponsor	University of Oxford Joint Research Office [name]		
Funder	Amgen		
Study Design	Multiple-site, cross-sectional, observational study		
Study Participants	Adult Patients with psoriatic arthritis recruited from rheumatology clinics		
Sample Size	500		
Planned Study Period	This study is a cross-sectional study with only 1 visit involved per participant. Total study period 24 months		
Planned Recruitment period	1 st January 2021 – 31 st December 2021		
	Objectives	Outcome Measures	Timepoint(s)
Primary	Assess the influence of PsAID-12 score on likelihood of treatment escalation	PsAID-12 questionnaire Treatment escalation recorded in clinic, with reason for decision	Cross-sectional
Secondary	Evaluate the impact of reviewing the PsAID-12	Likert scale “Beyond your usual clinical assessment, how did your review of the patient’s	Cross-sectional

	questionnaire on the physician's decision to change treatment	PsAID-12 questionnaire responses impact on your therapy decision for this patient”	
	Assess the effects of other factors that influence the likelihood of treatment escalation	Treatment escalation in clinic Factors include patient gender, disease duration, comorbidities, physician age, disease activity and PROs. Specifically addressing the impact of PsAID-12 individually and above other factors	Cross sectional
	Determine which factors physicians feel influence treatment decisions in routine practice	NRS of the perceived importance of individual factors that may influence individual treatment decisions	Cross sectional
	Evaluate patient satisfaction and perceived patient effectiveness in the consultation and examine how this links to PsAID-12 score and whether treatment is changed	CollaboRATE and PEPPi questionnaires and their relationship to PsAID-12 scores and treatment change	Cross sectional
	Explore the physicians' views on the use and value of the PsAID-12 tool	Qualitative reports by physicians with themes identified retrospectively	
Intervention(s)	This is an observational study and no interventions will be performed other than routine clinic assessments.		
Comparator	Not applicable		

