7. STUDY DESIGN

This is an observational, cross-sectional study addressing the factors influencing treatment decisions in patients with PsA. Participants will be treated as usual in their routine clinical practice, but decisions on treatment will be recorded – whether treatment is escalated, unchanged or reduced, and why.

The study will be conducted in 25 rheumatology centres in Europe (UK, France, Germany, Spain and Italy) with five centres in each country. Each participant will only attend for one single study visit which is likely to last around 30 minutes in total. This will be alongside their routine clinic visit. The PsAID-12

questionnaire will be implemented on a tablet computer but the remaining outcomes will be collected on paper CRFs and transferred to a database for analysis.

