11.2. Outcome variables

The primary outcome variable is whether an escalation in current treatment for PsA is required. An escalation in treatment consists of one or more of the following:

- Increase in dose of current medication
- Increase in frequency of dose administration
- Change in route of administration (i.e. from oral to sc MTX if dose not reduced)
- Initiation of a new medication in addition to existing therapy (including steroid >5mg prednisolone, conventional, targeted synthetic, or biologic DMARD)
- Initiation of a new medication as a switch from existing therapy (including steroid >5mg prednisolone, conventional, targeted synthetic, or biologic DMARD)

Reduction of therapy will also be collected, defined as any of the following:

- Decrease in dose of current medication
- Decrease in frequency of dose administration
- Change in route of administration, where not covered as described under “Escalation” above
- Stopping a medication

If the patient is retained on the same treatment regimen as they were on before the clinic visit, this will be considered as “No change”

Details of treatment prior to (at the start of) the appointment and subsequent to the appointment (including any treatment changes) will be collected.

Secondary outcomes comprise the following:

Patient data:

- PsA impact of disease (PsAID-12) scores
- Patients' satisfaction with consultation as measured by the COLLABORATE scores
- Perceived efficacy on patient-physician interaction score (PEPPI)
- Other assessments performed (see 9.7) will be used for the analysis of factors affecting treatment decisions but do not represent outcomes per se

Physician data:

- Physician's opinion of the reasons driving the treatment decision
 - Assessment of tender/swollen joints/enthesis
 - Assessment of skin and nail psoriasis
 - Marker of systemic inflammation (e.g. CRP)
 - Routine patient reported outcomes (e.g. patient global or pain scores)
- Physician's opinion of how the PsAID-12 questionnaire responses influenced the treatment decision today.

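### The link of CollaboRATE and PEPPI to PsAID-12 and treatment change is planned only as tables or graphs, with no effect estimate, confidence interval or clinic term

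*Combined protocol and SAP*

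**What the plan says.** The study title in the synopsis (section 3) sets satisfaction beside treatment intensification: "How does PsAID implementation affect treatment intensification and patient satisfaction in PsA". Section 6 makes it a secondary objective, which is to evaluate satisfaction and perceived efficacy and to "examine how this links to PsAID-12 score and change in treatment". The outcome measure given there is "CollaboRATE and PEPPi questionnaires and their relationship to PsAID-12 scores and treatment change". Section 5 also describes satisfaction as a secondary aim.

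Section 11.3 gives the method. For CollaboRATE, "the relationship between these scores and the decision to change treatment, and other key outcomes, will be investigated in summary tables and/or graphs". PEPPI has a sentence to the same effect: its relationships too "will be investigated in summary tables and/or graphs". Neither sentence names PsAID-12, but section 11.2 lists "PsA impact of disease (PsAID-12) scores" among the secondary outcomes, so it is fair to count it among the other key outcomes.

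For the primary outcome, the same section specifies a logistic regression for the effect of PsAID-12 "on the probability of modifying treatment, after adjusting for clinic", with an odds ratio and 95% confidence interval. On the setting, section 7 says: "The study will be conducted in 25 rheumatology centres in Europe (UK, France, Germany, Spain and Italy) with five centres in each country". Section 11.1 describes the statistical section as an outline and refers to a separate, more detailed SAP, which is not among the documents available.

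**The concern.** The objective is about a relationship, and a relationship needs an effect measure and some statement of its precision. Mean scores tabulated by treatment decision or by PsAID-12 band show a pattern. They do not show how much of it survives once the centre is accounted for.

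The centre is a plausible source of such patterns. Patients are rating a consultation, and a site may have only one or a few physicians (section 8.1). Questionnaires are completed in the local language (section 8.2.1). Centres are chosen partly for variety of setting (section 11.12). PsAID-12 levels and the readiness to change treatment may differ between the same centres. A pooled table then mixes two things: whether patients with higher impact are more or less satisfied than others in their own clinic, and whether clinics or countries with higher impact give higher or lower ratings. The site comparison in section 11.12 covers recruitment, demographics and disease characteristics. It does not mention satisfaction.

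**Working it through.** **Inputs from the documents.** N = 500, which section 11.4 obtains from 15 factors × 10 events / 0.30 = 500. There are 25 centres (section 7), so on average 500/25 = 20 patients each. The treatment-change rate is 30% (section 11.4). No sample-size figure in the plan concerns satisfaction, so there is no planned figure to reproduce for this objective.

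**Assumptions.** The documents give no ICC for any of these variables and no between-clinic correlation. The ICC was varied from 0 to 0.20 (the same for both variables), and the between-clinic correlation ρ was set at 0, 0.5 or 0.8.

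**Step 1: satisfaction against PsAID-12.** Each score is a clinic component with variance ICC plus a patient component with variance 1 − ICC. Clinic components correlate at ρ and patient components are independent, so there is no association within any clinic. The expected crude correlation is then ρ × ICC. For ρ = 0.5 this is 0.5 × 0.05 = 0.025, 0.5 × 0.10 = 0.05 and 0.5 × 0.20 = 0.10. In 4,000 simulated studies per setting, with clinic as a fixed effect in the adjusted analysis:

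| ICC | ρ | Mean crude r | Crude p<0.05 | Clinic-adjusted p<0.05 |
|---|---|---|---|---|
| 0.05 | 0 | 0.00 | 5.2% | 4.4% |
| 0.05 | 0.5 | 0.023 | 8.7% | 5.1% |
| 0.05 | 0.8 | 0.039 | 14.5% | 4.5% |
| 0.10 | 0 | 0.00 | 7.1% | 4.7% |
| 0.10 | 0.5 | 0.048 | 20.2% | 4.7% |
| 0.10 | 0.8 | 0.076 | 39.8% | 5.1% |
| 0.20 | 0 | 0.00 | 13.1% | 4.7% |
| 0.20 | 0.5 | 0.095 | 54.9% | 4.7% |
| 0.20 | 0.8 | 0.153 | 85.7% | 4.5% |

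At ICC 0 both analyses stay at about 5%.

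**Step 2: satisfaction against treatment change (30% changed).** At ρ = 0.5 and ICC 0.05, 0.10 and 0.20, the spurious mean difference is 0.04, 0.09 and 0.17 SD, and the crude comparison reaches p<0.05 in 8.0%, 17.4% and 44.2% of studies. At ρ = 0 the rates are 5.6%, 6.6% and 10.8%. At ρ = 0.8 and ICC 0.20 the difference is 0.27 SD and the rate 76.1%. After clinic adjustment the rate lies between 4.3% and 5.4% in every setting.

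**Step 3: masking.** With equal ICCs and a within-clinic correlation r_w, the crude correlation is ρ × ICC + r_w × (1 − ICC). With ρ = −0.5, ICC = 0.20 and r_w = 0.125, it is −0.10 + 0.10 = 0. A real association would not show in a pooled table.

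**Step 4: price of adjustment.** The correlation detectable with 80% power at two-sided 5% is tanh[(1.96 + 0.8416)/√(n − k − 3)], where k is the number of adjusting terms. Crude: tanh(2.8016/√497) = 0.125. With 24 clinic contrasts: tanh(2.8016/√473) = 0.128.

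**The case against.** The case for leaving the plan as it is has real weight.

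- **The text does not say pooled or unadjusted.** Tables can be split by clinic or country, so pooling is an inference. This stands, and the concern is therefore conditional. Splitting would not fully answer it: 25 tables of about 20 patients give no combined within-clinic estimate.
- **A separate SAP will add detail.** It may close the gap. But section 11.3 is not silent on these scores. It states a method, and a more detailed SAP could simply elaborate the tables.
- **The objective is secondary and no test is planned.** This stands. The rejection rates show how easily a pooled pattern could mislead. They are not the error rate of anything in the plan. The correlations behind them at ρ = 0.5 are small: 0.025² to 0.10², or about 0.06% to 1% of variance.
- **Clinic in the primary analysis may reflect sampling within centre.** The plan never calls clinic a confounder, and the objective is not confined to within-clinic association. This too stands. The different treatment of clinic in the two analyses is an unexplained choice and not a contradiction.
- **Clinic adjustment leaves patient-level confounding, such as disease activity.** It does, so the adjusted estimates remain exploratory.

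**Conclusion.** The point holds as a cheap improvement. For a stated objective about associations, section 11.3 offers description without an effect measure, interval or clinic term, in a study of 25 centres across five countries. If the tables pool centres, the spurious correlation is about 0.025 to 0.10 under assumed ICCs of 0.05 to 0.20 and ρ = 0.5, and a crude correlation would reach p<0.05 in about 9% to 55% of studies. At ρ = 0 the range is about 5% to 13%, and if clinics do not differ the problem disappears. All of this rests on ICCs and correlations that the documents do not give.

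Two stronger readings are tempting and are not supported. A reader might infer that the plan commits to a crude pooled analysis with an inflated type I error; the documents neither say the tables are pooled nor plan a test. A reader might also infer from the title that half of the study question is left without a valid answer. Sections 5 and 6 make satisfaction a secondary aim, no sample size rests on it, and means or percentages in tables are still estimates, though their clinic handling and precision are unspecified.

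**What to change.** In section 11.3, and in the separate SAP, keep the tables and graphs as description and add prespecified clinic-adjusted models:

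- Use logistic regression for the CollaboRATE top score, and linear regression for the CollaboRATE mean and the PEPPI total.
- Enter clinic as a stratum or random effect. The 4% to 5% rates above are for a fixed clinic effect. A random intercept alone lets some between-clinic information into the coefficient, so if it is chosen, add the clinic mean of the explanatory variable.
- Fit PsAID-12 and treatment change in separate models. Section 5 hypothesises that PsAID-12 influences treatment, so a joint model would adjust PsAID-12 for its own supposed consequence. Label any joint model as supplementary.
- Report estimates with 95% confidence intervals as exploratory associations.

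The cost is a few extra models on data already collected and a very small loss of precision (detectable correlation 0.128 against 0.125). No extra patients or visits are needed. Patient-level confounding remains and should be acknowledged in the report.
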